1.5 Study Synopsis

Protocol Title	A prospective, double blind, randomized, placebo-controlled clinical trial of intracoronary infusion of immunoselected, bone marrow-derived Stro3 mesenchymal precursor cells (MPC) in the treatment of patients with ST-elevation myocardial infarction
Sponsor	Mesoblast, Inc. [name] USA
Study Phase	2
Investigators and Clinical Sites	Approximately 25 clinical sites
Indication	De novo anterior wall myocardial infarction due to a lesion or occlusion of the left anterior descending (LAD) coronary artery.
Study Hypothesis	MPCs when administered intracoronary immediately after successful PCI with stenting in patients with first time acute anterior STEMI will result in amelioration of the early post-event inflammatory response and subsequent fibrotic scarring as well as promote the process of neo-angiogenesis in tissue where an ischemic condition exists or is developing. The net result will be: 
 decreased infarct size by short term protection of at-risk myocardium increased long term salvage of myocardium resulting in decreased adverse left ventricular (LV) remodeling.
Objectives	
Primary Objective:
 
 To determine the safety and feasibility of intracoronary allogeneic, immuno-selected, bone marrow-derived Stro3 MPC delivery in the treatment of subjects with STEMI undergoing PCI of the LAD coronary artery. 
Secondary Objectives:
 
 To explore a dose-response effect of intracoronary delivered MPC in the treatment of subjects with an anterior wall STEMI on LV remodelling, microvascular obstruction, and the relationship between time from onset of ischemic symptoms to primary PCI. To determine the effect of intracoronary delivery of MPC on infarct size reduction in the treatment of subjects with STEMI undergoing primary PCI of the LAD coronary artery. [REDACTED]

Study Design	
This is a prospective, double-blind, randomized, placebo-controlled study that will enroll approximately 105 subjects with de novo anterior STEMI due to a lesion involving LAD coronary artery who undergo primary PCI at approximately 25 clinical study sites.
 
This study will compare two doses of MPCs and a placebo control group. Study subjects will be randomly assigned in 1:1:1 fashion to receive either 12.5 Million or 25 Million MPCs or placebo (saline). Each group will have approximately 35 subjects.
 
Potential subjects will be approached by a site investigator prior to PCI and must sign an informed consent form before initiation of the cardiac catheterization procedure in order to participate in this trial. Following successful and uneventful PCI and stenting of the culprit LAD lesion, the subjects will be randomized. The randomization and treatment assignment will be obtained from an interactive voice-response system (IVRS/interactive web response system (IWRs)). The following stratification for duration of cardiac ischemia will be performed to ensure balanced randomization across the treatment groups:
 
• ≤ 2 hours• > 2 hours to ≤ 6 hours• > 6 to ≤ 12 hours. 
Eligible subjects will receive intracoronary delivery of the assigned treatment infused via a microcatheter into the stented culprit artery. The subjects randomized to MPCs will be infused at an infusion rate of 2 ml/min over approximately 60 minutes, including line flush [2.5×10^5 MPCs/min (12.5 M), 5.0×10^5 MPCs/min (25 M)]. The subjects randomized to placebo will be infused placebo solution at 2 mL/min over approximately 60 minutes, including line flush (0 MPCs/min). The MPC product (12.5M and 25M MPCs) and the placebo solution will be diluted in 100mL 0.9% saline solution prior to infusion. The Sponsor will provide all sites with blinded treatment cryovials, which contain the different doses of MPCs or placebo solution.
 
An intracoronary (IC) bolus of glyceryl trinitrate (GTN)/nitroglycerin (NTG) (100-200 mcg) should be administered (blood pressure permitting) prior to the Thrombolysis in Myocardial Infarction (TIMI) flow assessment during the investigational agent infusion period as well as after completion of the investigational agent infusion and immediately prior to the final coronary

---------------------	---

	
angiographic imaging.
 
After approximately 50% of the intracoronary infusion of investigational agent has been completed, an angiographic determination of coronary flow will be performed. The following guidelines will be used to determine if the remaining investigational agent should be infused:
 
• The study infusion should be continued if either TIMI 2 or TIMI 3 flow is present in the absence of ALL of the following:
○ Sustained hypotension not responsive to fluid administration;○ Clinical signs/symptoms indicating an acute cerebrovascular event;○ Re-elevation of ST-segments if previously resolved with PCI;○ Onset of the subject's symptoms of myocardial ischemia unresponsive to appropriate interventions;○ Two episodes of sustained ventricular tachycardia (VT)/ventricular fibrillation (VF) requiring cardioversion (infusion can continue if a single episode of sustained VT/VF requiring cardioversion occurred). 
If for any reason, the site investigator withdraws a randomized subject prior to infusion of the investigational agent, the reason for early termination and data from the screening visit will be entered into the eCRF by the study site. The subject will not remain in the study. If for any reason, a subject's study infusion is halted due to safety considerations, the subject will remain in the study. A subject who prematurely withdraws from the study, post-study infusion, will remain in the study.
 
Evaluation for safety will be performed for up to 24 months post infusion. Subjects will undergo cardiac magnetic resonance imaging (cMRI) and 2-D echocardiography (ECHO), Holter monitoring, clinical evaluation and laboratory testing.
 
cMRI, ECHO monitoring will be performed at 2-7 days post infusion of study agent (MPCs or Placebo), as well as at Day 30 and at Month 6 after the procedure. Holter monitoring will be performed at 14 and 30 days, 3 and 6 months after the procedure. Clinical evaluation and laboratory testing will be performed at 6, 12, 18 and 24 hours post infusion of study agent (MPCs or Placebo), during the index hospitalization as well as at 14 and

--	--

	
30 days and 3, 6, 12, 18 and 24 months after the procedure as outlined in Table 2 Schedule of Assessments and Procedures.
 
An independent Data Safety Monitoring Board (DSMB) will review all relevant acute peri-procedural data, serious adverse events (SAE), other adverse events (AE), and efficacy data (if requested) periodically dependent on subject enrollment, and advise the Executive Steering Committee (ESC) regarding the progression of the study.
 
The ESC will consist of the Coordinating Investigator, site investigators and representatives of and advisors to the Sponsor.
 
A Clinical Events Committee (CEC) will review appropriate source documents and adjudicate (blinded per a priori procedure) all major adverse cardiovascular and cerebrovascular events (MACCE) defined as cardiovascular death, non-fatal myocardial infarction, non-fatal stroke, or cardiac hospitalization due to heart failure. Target vessel (or other vessel) revascularization post index cardiac catheterization and new or worsening heart failure during the index hospitalization will be tracked as “Adverse Events of Special Interest” rather than MACCE.
 
Subjects, Site personnel, Investigators will remain blinded until after all safety follow-up is completed. The DSMB may choose to be unblinded.
 
The DSMB safety reviews to assess the frequency of total MACCE will be performed after the initial 15, 30, 60, and 90 subjects have been observed at Day 30 post the index cardiac catheterization.
 
The final safety analysis will be performed at 24 months for all patients.

Population	Subjects age 18 and above who have been successfully treated within 12 hours of the onset of ischemic symptoms with standard care for a de novo STEMI (PCI and stent placement) involving the LAD coronary artery.
Efficacy Endpoints	
Primary Efficacy Endpoint:
 
 • The primary efficacy endpoint is the change in LV end-systolic volume (LVESV) as assessed by cardiac MRI from baseline to 6 months post investigational agent infusion in each MPC treatment group compared with the Placebo group.

	
Secondary Efficacy Endpoints:
 
• The change in LVESV as assessed by 2D-echocardiography from baseline to 6 months post investigational agent infusion.• The change in relative infarct size as assessed by late contrast enhancement MRI (% infarct volume/total LV tissue volume) from baseline to 6 months post investigational agent infusion.• Additional functional efficacy endpoints will be assessed with the following diagnostic studies:
○ Cardiac MRI at 2-4 days, 30 days and at Month 6.
○ LVEF○ LVESV○ LVEDV○ Left ventricular wall thickness and thickening in all segments including infarct area○ Regional wall motion score○ Myocardial microvascular obstruction measured as reduced signal intensity in the region of interest○ MI size measured in the region of interest as late contrast enhancement○ Myocardial salvage index○ 2D echocardiogram at 2-4 days, 30days and at Month 6.
○ LVEF○ LVESV○ LVEDV○ Cardiac dimensions (LVESD/ LVEDD)○ Regional wall motion score index• If there is no difference between the MPC groups (using a test with alpha= 0.1) in the effect on LVESV then the pooled MPC group will be compared to the Placebo group for all functional parameters.○ A subset analysis that corresponds to the stratification used during randomization will be performed. Stratification will be based on the following categories defined as time from onset of AMI symptoms to PCI:
○ ≤ 2 hours○ > 2 to ≤ 6 hours○ > 6 to ≤ 12 hours.• In addition, a subset analysis will be evaluated at the following ischemia duration time points:
○ ≤ 6 hours○ > 6 to ≤ 12 hours
--	--

	
 • NT-Pro-BNP serum levels (as a biomarker for heart failure) at baseline, days 2-4 and 30, and months 3, 6, 12 and 24 • Score changes for TIMI Flow Grade and TIMI Myocardial Perfusion Grade assessments at the following day 0 time points: 
 ◦ pre-PCI, ◦ immediately post-PCI, ◦ after approximately 50% of intracoronary infusion of investigational agent, ◦ at completion of intracoronary infusion of investigational agent.
Safety Endpoints	
All safety end points will be assessed from subject randomization through up to 24 months post investigational agent infusion:
 
 • SAE /AE rates • Occurrence of MACCE events including: 
 ◦ Cardiovascular death ◦ Non-fatal myocardial infarction ◦ Non-fatal stroke ◦ Cardiac hospitalization due to heart failure • Target vessel (or other vessel) revascularization post index cardiac catheterization and new or worsening heart failure during the index hospitalization will be tracked as “Adverse Events of Special Interest”. • Total number of subjects with documented ventricular arrhythmia (sustained and non-sustained VT/VF) throughout the study period. • Angina pectoris as defined by Canadian Cardiovascular Society (CCS) clinical clarification. • New York Heart Association (NYHA) Class. • Telemetry/48 hour Holter monitoring (during hospital admission and at 14 and 30 days, 3 and 6 months follow-up time points) with assessment of occurrence of ventricular arrhythmia. • TIMI Flow Grade and TIMI Myocardial Perfusion Grade following intracoronary infusion of the MPC cell solution compared with placebo • Physical examinations, monitoring of vital signs (heart rate, respiratory rate, BP, and temperature). • Results of clinical laboratory tests (hematology, serum chemistry, inflammatory markers), and immunogenicity assays; (flow cytometry Class I and Class II HLA percent reactivity % with specificity, antibovine and antimurine antibody analysis).

	
AE will be collected after a subject has been randomized. The AE will be graded according to the protocol as “mild”, “moderate”, “severe” and will be classified with the Medical Dictionary for Regulatory Activities.
 
An independent DSMB will review all safety and relevant clinical data at regular intervals in accordance with their charter. Based on its findings, the DSMB will make recommendations regarding study continuation, enrollment and/or study modification(s).

Feasibility Endpoint	
Feasibility of the infusion of the investigational agent will be monitored by measurement of TIMI flow and perfusion measurements prior to, during (after approximately 50% of total investigational agent volume infused) and following the investigational agent infusion after successful PCI and stenting.

Clinical Endpoints	
Clinical Endpoints will be assessed throughout the index hospitalization as well as at outpatient visits at 14 and 30 days, and at 3, 6, 12, 18 and 24 months after the index cardiac catheterization procedure, including:
 
 • Occurrence of MACCE including: 
 ◦ Cardiovascular death ◦ Non-fatal myocardial infarction ◦ Non-fatal stroke ◦ Cardiac hospitalization due to heart failure • Target vessel (or other vessel) revascularization post index cardiac catheterization and new or worsening heart failure during the index hospitalization will be tracked as “Adverse Events of Special Interest”. • Total number of subjects with documented ventricular arrhythmia (sustained and non-sustained VT/VF) throughout the study period. • Angina pectoris as defined by Canadian Cardiovascular Society (CCS) clinical clarification. • Functional status will be classified by the NYHA criteria.
Planned Analysis of Efficacy and Safety	
The primary efficacy analysis for LVESV will be performed using cMRI collected data. The secondary efficacy analyses for LVESV will be performed using ECHO data alone, as well as ECHO data as a substitute for missing cMRI data at baseline and/or at Month 6.
 
In the latter case, a regression equation will be determined between measurements for LVESV-cMRI and LVESV-ECHO over a range of values. Whenever appropriate and based on LVESV-ECHO values generated using the regression equation, a LVESV-ECHO “corrected” value will be determined and used as

	
a replacement for missing value for LVESV-cMRI.
 
When all enrolled subjects have completed the study through Visit 9 (Month 6), an unblinded analysis of the safety and primary and secondary efficacy endpoints will be conducted.
 
The primary and secondary efficacy analyses will be performed using data collected through Visit 9 (Month 6). Safety analyses will be performed on all available data through Visit 12 (Month 24) at the time of conduct of the efficacy analysis. In addition, the final safety analysis will be performed at 24 months for all patients.
 
No additional efficacy data will be collected beyond Visit 9 (Month 6) except for cardiac biomarkers.

Inclusion Criteria	
Blinded Study Personnel and Participants
 
Subjects, Site personnel, Investigators will remain blinded until after all safety follow-up is completed. The DSMB may choose to be unblinded.
 
Unblinded Study Personnel
 
Pre-specified unblinded clinical operations and biometrics team members at both the vendor and sponsor will have access to the unblinded efficacy results.
 
These pre-specified unblinded team members will be identified prior to the analysis being conducted and they will not have any operational responsibility for the conduct of the study.
 
An independent unblinded statistician from [REDACTED] will support the DSMB by providing Open and Closed Reports to the DSMB independent statistician based on the best available data and other information to the DSMB.
 
Subjects will be entered into this study only if they meet ALL of the following criteria:
 
1. Willing and able to understand and sign the Informed Consent Form (ICF).2. Males or females \geq 18 years.3. Clinical symptoms consistent with AMI (pain, etc.) for a maximum of 12 hours from onset of symptoms to completion of PCI.4. De novo anterior AMI [REDACTED]

	
3. Unsuccessful revascularization of culprit artery defined as TIMI 1 or 0 flow or residual diameter stenosis of $\geq 20\%$ by on line QCA analysis.4. Need for staged treatment of coronary artery disease, or other interventional or surgical procedures to treat heart disease 5. Cardiogenic shock or hemodynamic instability within 24 hours prior to randomization, 8. Prior PCI involving the LAD.9. Malignancy within last 3 years from screening. The subject has had an active malignancy, within the past 3 years except for cervical carcinoma in situ or non-melanoma skin cancer that has been definitively treated. 11. Pacemaker, ICD or any other contraindication for cMRI. This is inclusive of patients with an MRI compatible device that was implanted prior to the potential qualifying event. 15. Known hypersensitivity to any radiographic contrast16. Known hypersensitivity to dimethyl sulfoxide (DMSO),
--	---

	
18. Prior participation in any other investigational drug trial in the past 30 days.
 
19. Pregnant or lactating women.

signs, laboratory parameters, and physical examination findings will be reported as appropriate and summarized.

The following stratification for duration of cardiac ischemia will be performed to ensure balanced randomization across the treatment groups:

- ≤ 2 hours
- >2 hours to ≤ 6 hours
- >6 to ≤ 12 hours

To detect a change from baseline to Month 6 treatment effect of 10.0 ml for LVESV (SD 14 ml), [REDACTED]

[REDACTED] as well as published clinical data^{1-3, 58, 59}, with a two-sided 5% significance level and a power of 80%, a sample size of 105 subjects will be necessary, given the observed dropout rate of approximately 4%. Of these, approximately 70 will receive MPCs (35 to receive 12.5 M MPC and 35 to receive 25M MPC) and 35 will receive placebo and act as control subjects.

1.6 Assessments and Procedures

Table 2: Schedule of Assessments and Procedures

Study Day	Visit 1	Visit 2	Visit 3	Visit 4	Visit 5	Visit 6	Visit 7	Visit 8	Visit 9	Visit 10	Visit 11	Visit 12	Early ^r Term
	Day 0 AMI, Pre Study Infusion	Day 0 Immediate Post Study Infusion	6, 12, 18 Hours Post Study Infusion ± 1Hour	24 Hours Post Study Infusion ± 2Hours	2 - 7 Days Post Study Infusion (or Until Hosp D/C)	14 Days Post Study Infusion ± 3 Days	30 Days Post Study Infusion ± 7 Days	3 Mos. Post Study Infusion ± 7 Days	6 Mos. Post Study Infusion ± 14 Days	12 Mos. Post Study Infusion ± 14 Days	18 Mos. Post Study Infusion ± 30 Days	24 Mos. Post Study Infusion ± 30 Days	
Assessment													
Informed consent and HIPAA	X												
Review of inclusion/exclusion criteria	X												
Medical and Surgical Histories ^a	X												
Physical examination ^b	X			X	X ^l	X	X	X	X	X		X	X
Concomitant medications, including vaccinations	X	X	X	X	X ^l	X	X	X	X	X	X	X	X
Vital signs ^c	X		X	X	X ^l	X	X	X	X	X		X	X
12-lead ECG	X	X		X	X ^l		X	X	X	X		X	X
Telemetry Monitoring		X	X	X	X ^l								
Basic Metabolic Profile ^d	X				X ^h	X	X	X	X	X		X	X
Troponin-I or Troponin-T	X		X	X	X ^l								
CK-MB	X		X	X	X ^u			X	X	X			
Non-fasting Lipid	X							X	X	X		X	X

	Visit 1	Visit 2	Visit 3	Visit 4	Visit 5	Visit 6	Visit 7	Visit 8	Visit 9	Visit 10	Visit 11	Visit 12	Early ^r Term
Study Day	Day 0 AMI, Pre Study Infusion	Day 0 Immediate Post Study Infusion	6, 12, 18 Hours Post Study Infusion ± 1Hour	24 Hours Post Study Infusion ± 2Hours	2 - 7 Days Post Study Infusion (or Until Hosp D/C)	14 Days Post Study Infusion ± 3 Days	30 Days Post Study Infusion ± 7 Days	3 Mos. Post Study Infusion ± 7 Days	6 Mos. Post Study Infusion ± 14 Days	12 Mos. Post Study Infusion ± 14 Days	18 Mos. Post Study Infusion ± 30 Days	24 Mos. Post Study Infusion ± 30 Days	
profile ^e													
hsC-Reactive Protein	X				X ^h	X	X	X	X	X		X	X
Hepatic Function Profile ^f	X				X ^h	X	X	X	X	X		X	X
Complete blood count with platelets and differential	X				X ^h	X	X	X	X	X		X	X
Flow cytometry Class I and Class II antibodies (%) PRA) with specificity	X					X	X	X	X	X			X ^o
Anti-murine and Anti-bovine antibodies	X					X	X	X	X	X		X	X
NT-Pro Brain Natriuretic Peptide, type B	X				X ^h		X	X	X	X		X	X
Pregnancy test ^g	X							X					X
Primary PCI with stent placement	X												
2-D Echocardiogram ^h					X ^h		X		X				
Selective Coronary Angiogram of Target Vessel	X												
TIMI flow and perfusion measurements ^j	X	X											
QCA culprit vessel	X												

	Visit 1	Visit 2	Visit 3	Visit 4	Visit 5	Visit 6	Visit 7	Visit 8	Visit 9	Visit 10	Visit 11	Visit 12	Early ^r Term
Study Day	Day 0 AMI, Pre Study Infusion	Day 0 Immediate Post Study Infusion	6, 12, 18 Hours Post Study Infusion ± 1Hour	24 Hours Post Study Infusion ± 2Hours	2 - 7 Days Post Study Infusion (or Until Hosp D/C)	14 Days Post Study Infusion ± 3 Days	30 Days Post Study Infusion ± 7 Days	3 Mos. Post Study Infusion ± 7 Days	6 Mos. Post Study Infusion ± 14 Days	12 Mos. Post Study Infusion ± 14 Days	18 Mos. Post Study Infusion ± 30 Days	24 Mos. Post Study Infusion ± 30 Days	
Cardiac MRI ^p					X ^h		X		X				
Investigational Agent Infusion ^q	X												
Hospital Discharge with 48 hr. Holter					X								
Killip Class	X												
48 hour Holter Monitoring						X	X	X	X				
Canadian Cardiovascular Society Angina Classification					X ^h		X	X	X		X	X	
NYHA classification					X ^h		X	X	X		X	X	
Randomization	X												
AE/SAE Assessment ^{kk}	X	X	X	X	X ^l	X	X	X	X	X	X	X	
Telephone assessment											X		

- a. Previous Medical History includes medical, surgical, medication, alcohol, drug, and tobacco use, known renal and/or pulmonary disease recent immunizations/vaccinations, blood transfusions and number of pregnancies (females only)
- b. Physical examination to include but not limited to examination of the cardiac, pulmonary, neurologic (including but not limited to mental status) and gastrointestinal systems as well as the measurement of weight. Height and body mass index (BMI) to be determined only at screening. At Visit 5 (Days 2-7 post study infusion), weight should only be measured on Target Day 3 (+/- 1 post study infusion).
- c. Vital signs consist of blood pressure (BP), temperature, heart rate, and respiratory rate.
- d. Basic Metabolic Profile (sodium, potassium, chloride, CO₂, blood urea nitrogen, glucose, creatinine, calcium, calculated GFR)
- e. Non-fasting Lipid Panel (cholesterol, triglycerides, HDL, LDL)

- f. Hepatic Function Profile (total protein, albumin, total bilirubin, direct bilirubin, alanine aminotransferase (ALT), aspartate aminotransferase (AST), alkaline phosphatase)
- g. Urine Pregnancy testing at screening; serum pregnancy testing at follow-up study visits
- h. Target Day 3 (+/- 1 day) post study infusion
- i. Performed daily
- j. During infusion of the Investigational Agent, TIMI flow and perfusion measurements should be evaluated and recorded prior to IA infusion, when approximately 50% of the Investigational Agent has been infused, and immediately post investigational agent infusion.
- k. AE/SAE assessments should be collected from time of randomization
- l. 12 lead ECG should be measured on Day 2 and prior to hospital discharge
- m. 2D echo will be performed through 6 month follow-up period only. 2D echo will be performed without contrast
- n. For subjects that receive Investigational agent and discontinue prior to Visit 9 (Month 6) cardiac MRI will not be obtained as part of the early termination visit.
- o. Only for subjects that receive Investigational agent and discontinue prior to Visit 10 (Month 12)
- p. cMRI will be performed through 6 month follow-up period only. Please refer to the study imaging manual for details on MRI contrast agents.
- q. To be performed only if all inclusion/exclusion criteria are adequately satisfied.
- r. An ET visit will include the following tests: Physical examination, record of concomitant medications, vital signs measurement, 12-lead ECG, basic metabolic profile, non-fasting lipid profile, hs C-reactive protein, hepatic function profile, CBC with differential and platelets, Flow cytometry anti-HLA Class I and Class II antibodies for subjects discontinued prior to visit 10 (Month 12), Anti-murine and Anti-bovine antibodies, NT-Pro BNP, serum pregnancy testing, Canadian Cardiovascular society Angina Classification, NYHA classification and NYHA classification. cMRI and ECHo are not required at an ET visit.

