After approximately 50% of the intracoronary infusion of investigational agent has been completed, an angiographic determination of coronary flow will be performed. The following guidelines will be used to determine if the remaining investigational agent should be infused:

- The study infusion should be continued if either TIMI 2 or TIMI 3 flow is present in the absence of ALL of the following:
 - Sustained hypotension not responsive to fluid administration;
 - Clinical signs/symptoms indicating an acute cerebrovascular event;
 - Re-elevation of ST-segments if previously resolved with PCI;
 - Onset of the subject's symptoms of myocardial ischemia unresponsive to appropriate interventions;
 - Two episodes of sustained ventricular tachycardia/ventricular fibrillation requiring cardioversion (infusion can continue if a single episode of sustained VT/VF requiring cardioversion occurred).

If for any reason, the site investigator withdraws a randomized subject prior to infusion of the investigational agent, the reason for early termination and data from the screening visit will be entered into the eCRF by the study site. The subject will not remain in the study. If for any reason, a subject's study infusion is halted due to safety considerations, the subject will remain in the study. A subject who prematurely withdraws from the study post study infusion will remain in the study.

Evaluation for safety will be performed for up to 24 months post infusion. Subjects will undergo cardiac magnetic resonance imaging (cMRI) and 2-D echocardiography (ECHO), Holter monitoring, clinical evaluation and laboratory testing.

cMRI, ECHO monitoring will be performed at 2-7 days post infusion of study agent (MPC or Placebo), as well as at Day 30 and at Month 6 after the procedure. Holter monitoring will be performed at 14 and 30 days, 3 and 6 months after the procedure. Clinical evaluation and laboratory testing will be performed at 6, 12, 18 and 24 hours post infusion of study agent (MPC or Placebo), during the index hospitalization as well as at 14 and 30 days and 3, 6, 12, 18 and 24 months after the procedure as outlined in [Table 2 Schedule of Assessments and Procedures](#).

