5.2 Subject Withdrawal

Subjects may withdraw from the study at any time, for any reason, without penalty, or prejudice to his or her future medical care. The investigator also has the right to withdraw subjects from the study in the event of intercurrent illness, adverse events, administrative, or other reasons.

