5.3 Withdrawal Procedures

In all cases, the reason(s) for withdrawal must be recorded on the eCRF. If a subject prematurely withdraws from the study post-study infusion for any reason, the investigator must make every effort to perform the evaluations described for the Early Termination visit. Since the ICF states that subjects that prematurely withdraw post study-infusion for any reason may also be contacted by telephone for follow-up safety information for up to 24 months post study infusion, unless the subject also specifically withdraws consent for this communication all subjects may also be contacted by telephone.

Figure 2: Randomization/Withdrawal

The randomization number assigned to a withdrawn subject will not be re-used.

Subjects who sign consent and are not randomized will be considered screen failures.

If during the course of the study a subject chooses to revoke his/her written authorization for the use and disclosure of Protected Health Information [PHI] (per HIPAA privacy ruling or other country and/or region specific law), the subject will then be withdrawn from the study as well (i.e., participation in this study is contingent upon an “active” written PHI use, collection, and disclosure authorization and only safety data will be collected as required by applicable laws. PHI collected prior to the date that the subject revokes his/her written authorization may still be used. In the event of a subject’s withdrawal, the investigator will promptly notify the medical monitor or designee and will make every effort to complete the assessments as indicated above for subjects who prematurely discontinue from the study. All withdrawn subjects will be followed until resolution of any AEs or until the unresolved AEs are judged by the investigator to have stabilized.

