11.5 Determination of Sample Size

To detect a treatment effect of 10.0 ml for LVESV (SD 14 ml), [REDACTED] as well as published clinical data ^{1-3, 58,59}, with a two-sided 5% significance level and a power of 80%, a sample size of 105 subjects will be necessary, given the observed dropout rate of approximately 4%. Of these, approximately 70 will receive MPCs (35 to receive 12.5 M MPC and 35 to receive 25M MPC) and 35 will receive placebo and act as control subjects.

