13.3 Changes to the Protocol

The investigator may not deviate from the protocol without a formal protocol amendment having been established and approved by an appropriate IRB/EC, and relevant regulatory authority if required, except when necessary to eliminate immediate hazards to the subject or when the change(s) involve only logistical or administrative aspects of the study. Any deviation may result in the subject having to be withdrawn from the study and rendering that subject non-evaluable.

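### An infused subject can be withdrawn from the study before Month 6 with no provision for the Month 6 cMRI or echo, so primary-endpoint data can be lost avoidably, and the passages on withdrawn subjects conflict.

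*Combined protocol and SAP*

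**What the plan says.** Section 6.1.1 describes a single intracoronary infusion, given on Day 0. Section 8.1 makes the primary efficacy endpoint the change in LVESV by cMRI from baseline to 6 months.

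Two sections allow an infused subject to be taken out of the study, not merely off treatment:

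- Section 5.2: "The investigator also has the right to withdraw subjects from the study in the event of intercurrent illness, adverse events, administrative, or other reasons".
- Section 13.3: "Any deviation may result in the subject having to be withdrawn from the study and rendering that subject non-evaluable".

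What follows withdrawal is set out in several places:

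- Section 6.1.1.13 lists the early termination procedures. Neither cMRI nor echo is among them, and both rows are blank in the early termination column of Table 2.
- Table 2, footnote n, on infused subjects who "discontinue prior to Visit 9 (Month 6) cardiac MRI will not be obtained as part of the early termination visit". Footnote r is softer: cMRI and echo are not required at that visit.
- Section 5.3: subjects who withdraw after infusion "may also be contacted by telephone for follow-up safety information for up to 24 months post study infusion", and adverse events are followed until they resolve or stabilise.

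Against this, section 4.3 says: "A subject who prematurely withdraws from the study post study infusion will remain in the study". The synopsis has the same sentence. Both also say that a subject whose infusion is halted for safety stays in the study.

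On analysis, section 11.8 applies the efficacy analyses to the ITT, full analysis and per-protocol populations. Section 11.2 bases the primary ANCOVA on collected cMRI data and gives no method for missing values. Using echo in place of missing cMRI is a secondary analysis.

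**The concern.** Once the infusion is over there is no study dosing left to stop. Withdrawal by the investigator at that stage changes only what is observed afterwards. A site that follows 5.2, 5.3 and 6.1.1.13 ends the visits and obtains no Month 6 LVESV, even from a subject who would attend. A site that follows 4.3 may keep the subject on schedule. Two sites could treat the same subject differently and both claim to follow the protocol.

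The ITT comparison of a Month 6 measurement is at stake. Each avoidable loss takes a randomised subject out of the primary ANCOVA. If the reason for leaving is linked to remodelling, as is plausible for adverse events or intercurrent illness, and the losses differ between arms, the estimated difference is biased. The plan's own fallback cannot repair this, because withdrawal removes the Month 6 echo along with the Month 6 cMRI.

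**Working it through.** **1. Passages side by side**

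| Question | 5.2, 13.3, 5.3, 6.1.1.13, Table 2 footnotes | Synopsis, 4.3 |
|---|---|---|
| Is the infused subject still in the study? | May be withdrawn from it | Stays in it |
| Imaging at early termination? | None listed; not obtained (n); not required (r) | Not addressed |
| Month 6 imaging after withdrawal? | Not provided for | Not stated |
| Other contact? | Telephone safety contact; adverse event follow-up | Not stated |

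No section schedules a Month 6 scan for a withdrawn subject, and none expressly forbids one.

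**2. The plan's sample size**

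Inputs from section 11.5: effect 10.0 ml, SD 14 ml, and "with a two-sided 5% significance level and a power of 80%, a sample size of 105 subjects will be necessary", with about 4% dropout. Section 4.3 gives 35 per arm.

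- Two-sample t-test (noncentral t): 32 per arm.
- Allowing for dropout: 32 / (1 − 0.04) = 33.3, so 34 per arm, and 3 × 34 = 102. This is within 3% of 105, so the stated figure is reproduced closely.
- Expected loss at 4%: 0.04 × 35 = 1.4 per arm; 0.04 × 105 = 4.2 in total.
- Power by the t-test: 83.8% with 35 per arm, 82.2% with 33.6 per arm (after 4% loss), 80.3% with 32 and 79.0% with 31.

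Loss of numbers alone is therefore not the problem at 4%.

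**3. Bias if the losses are selective and confined to one arm**

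Let m be the share of one arm without a Month 6 value and D the difference in mean LVESV change between its lost and observed subjects. The full-arm mean is (1 − m) × observed + m × lost, so the observed mean is off by m × D. The documents give no value for D. The range 14–40 ml is an assumption, from one planning SD to nearly three (40 / 14 = 2.9).

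For the two-sided error rate when there is no true effect, SE = 14 × √(1/35 + 1/(35(1 − m))). This is 3.38 ml at m = 4% and 3.44 ml at m = 10%. The error rate is P(Z > 1.96 − mD/SE) + P(Z < −1.96 − mD/SE).

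| m | D (assumed) | Bias m × D | Share of 10 ml | Two-sided error |
|---|---|---|---|---|
| 4% | 14 ml | 0.56 ml | 6% | 5.3% |
| 4% | 28 ml | 1.12 ml | 11% | 6.3% |
| 4% | 40 ml | 1.60 ml | 16% | 7.6% |
| 10% | 14 ml | 1.40 ml | 14% | 6.9% |
| 10% | 28 ml | 2.80 ml | 28% | 12.9% |
| 10% | 40 ml | 4.00 ml | 40% | 21.4% |

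If subjects doing worse are lost from an MPC arm, that arm looks better than it is. If they are lost from placebo, a true effect is diluted. With the same m and D in both arms, m × D cancels in the difference.

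**The case against.** A reader might infer that footnote n itself costs the trial its primary endpoint. It does not. It governs only the early termination visit, and a scan at, say, week 5 would not measure LVESV at Month 6. The loss comes from ending the visit schedule at withdrawal.

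A reader might also infer that the endpoint is lost by rule. The documents do not support that. The synopsis and 4.3 say the subject stays in the study, footnote r is weaker than footnote n, and section 6.3 promises vigorous efforts to obtain follow-up for all enrolled subjects. Section 6.3, however, deals with missed visits and does not restore imaging after withdrawal. Figure 2 in 5.3, on randomization and withdrawal, is not shown in the available text and may clarify what staying in the study means.

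A third tempting reading is that the subjects lost are those doing worst. That is plausible for adverse events or illness, but the documents do not show it. It does not follow for administrative or deviation withdrawals, and 13.3 says only that a deviation may lead to withdrawal. Subjects whose infusion is halted for safety are expressly kept.

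On size, the objection is largely right. The stated 4% covers every kind of dropout, including death, refusal and loss to follow-up, which new wording would not recover. The larger biases need selective loss of about 10% in one arm only, which the documents do not predict.

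What stands is the contradiction itself and the absence of any provision for Month 6 imaging in a willing subject.

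**Conclusion.** The point holds as an avoidable gap in collection of the primary endpoint, together with passages that must be reconciled. At the stated 4% dropout the possible bias is small: about 0.6–1.6 ml, or 6–16% of the 10 ml planned effect. At 10% it would be 1.4–4 ml. These figures rest on assumed gaps of 14–40 ml, on every loss being selective, and on loss in one arm only; they are not predictions. The share of post-infusion losses that would be investigator withdrawals is unknown, so the part that a change could recover is smaller than the total. It is not a fatal flaw, but the change is cheap and worth making.

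**What to change.** - Reconcile 5.2, 5.3, 6.1.1.13, 13.3 and Table 2 footnotes n and r with the sentences in the synopsis and 4.3 that keep a withdrawn subject in the study, and say what staying in means.
- Separate stopping study visits from withdrawal of consent or of authorization to use protected health information.
- State that an infused subject who stops visits before Month 6 for any other reason is asked to attend the scheduled Month 6 cMRI and echo, if they consent and have no contraindication.
- State that a deviation alone does not end outcome collection.

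A scan at the early termination visit is not needed. A pre-specified sensitivity analysis for outcome-related missing Month 6 values would be a useful complement, since some losses will remain.

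The cost is protocol wording and a few extra return visits. The scans are already scheduled for every subject and the sample size does not change. Some subjects will decline. The first scheduled cMRI is at Visit 5 (target Day 3), so a subject who leaves before it would still have no cMRI baseline.
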